7.3 Demographics and Baseline Characteristics

Subject demographics and baseline characteristics to be collected include sex, age, height, weight, vital signs, Fitzpatrick skin phototype, medical/surgical/cosmetic/dental procedure history, and prior medications.

7.4 Treatment Characteristics

Treatment characteristics will be evaluated by collecting information on anesthesia usage injection volume, and injection ease [REDACTED]

7.5 Summary of Methods of Data Collection

Electronic data capture and questionnaires will be used to collect study-specific information, such as subject and Investigator assessments. Completed eCRFs will be reviewed by the Investigator, and the designated monitor will verify the data. Investigators will provide access to hospital files, medical records, and other source documents containing subject clinical/medical information. Source document verification will be performed.

8. Statistical Procedures

A separate statistical analysis plan will be prepared to provide specifications for all analyses. The plan will be finalized and approved prior to clinical database lock.

Descriptive statistics will be presented for key outcome measures. Categorical variables will be summarized with response frequencies and percentages. Continuous variables will be summarized by number of subjects, mean, median, standard deviation, minimum, and maximum. Where appropriate, 2-sided 95% CIs for population mean, or population proportion, will be provided as part of the summary.

Every attempt will be made to collect complete data and limit the occurrence of missing data. No imputation of missing data is planned, except for sensitivity analyses described in Section 8.3.1 and to account for days with missing reports during the ISR duration discussed in Section 8.3.4.

8.1 Analysis Populations

The following analysis populations will be used in the analyses for this study:

- modified intent-to-treat (mITT) population: all randomized subjects who received treatment with cannula on 1 cheek and treatment with needle on the contralateral cheek
- safety population: all randomized subjects who received at least 1 study treatment
- per-protocol (PP) population: all mITT population subjects who did not have any significant protocol deviations that could affect the primary endpoint; a significant deviation that occurred after the primary endpoint would not lead to exclusion from the PP analysis

Analyses of safety variables will be performed on the safety population. Unless specified otherwise, all other analyses will be performed on the mITT population. The PP population will be used to perform PP sensitivity analyses for the primary and secondary effectiveness variables.

Analyses will be based on treatment received, regardless of randomization assignment (ie, “as treated” rather than “as randomized”), in order to prevent bias towards study success (non-inferiority) that would be due to randomization errors that reverse the direction of the paired comparison. In addition, the mITT population will be used to do an “as randomized” sensitivity analysis for the primary effectiveness variable. That will not be necessary for the PP population, since it will exclude subjects who were not treated as randomized.

8.2 Collection/Derivation of Primary and Secondary Effectiveness Assessments

8.2.1 Primary Effectiveness Variable

The primary effectiveness variable is the change from baseline (screening) to Month 1 in overall MFVDS based on EI assessment at each timepoint.

8.2.2 Secondary Effectiveness Variables

The secondary effectiveness variables include EI-assessed overall MFVDS responder rates and subject satisfaction score on the FACE-Q Satisfaction with Cheeks module at Month 1. An overall MFVDS responder is defined as a subject who improves at least 1 grade from baseline on the primary measure of overall MFVDS.

8.3 Hypothesis and Methods of Analysis

8.3.1 Primary Effectiveness Analyses

For the primary effectiveness analysis of change from baseline at Month 1 in EI-assessed overall MFVDS, the mean paired difference between treatment with cannula and treatment with needle, and its 95% CI based on the paired t-test will be calculated. If the upper confidence limit is less than 0.5, statistical non-inferiority will be concluded.

If there are any mITT subjects with missing scores for the primary effectiveness endpoint, the following 2 missing-data handling methods are pre-specified to use for missing-data sensitivity analysis of the primary effectiveness endpoint.

- 1) Multiple imputation [REDACTED]

- 2) Baseline observation carried forward (BOCF) to replace missing Month 1 scores

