
STUDY DESIGN: This is a multicenter, evaluator-blind, randomized, within-subject controlled, paired-comparison study of the safety and effectiveness of VOLUMA XC injectable gel using a cannula and needle for cheek augmentation to correct age-related volume deficit in the mid-face.
 
At screening, after written informed consent has been obtained, the Treating Investigator (TI) will document the subject's demographics, Fitzpatrick skin phototype, height, weight, vital signs, and medical, surgical, cosmetic, and dental procedures history. Female subjects of childbearing potential will undergo urine pregnancy testing. All subjects will complete the validated 5-item Satisfaction with Cheeks module of the FACE-Q questionnaire. The blinded Evaluating Investigator (EI) will rate the subject's mid-face deficit for the overall mid-face area, [REDACTED] on the validated 6-point photonumeric Mid-Face Volume Deficit Scale (MFVDS) (0 = none, 1 = minimal, 2 = mild, 3 = moderate, 4 = significant, 5 = severe) to determine eligibility for the study.
 
On the randomization/treatment day, subjects will have 1 cheek treated with VOLUMA XC injectable gel using a [REDACTED] cannula and the contralateral cheek treated using a [REDACTED] with a goal to achieve at least a 1-grade improvement. In the cheek randomized for cannula use, a maximum treatment with cannula should be attempted. [REDACTED]
 
[REDACTED] The side of treatment (ie, side of face for needle or cannula) will be randomized. The left side of face will be treated first for all subjects. For the cheek treated with cannula, an anesthetic agent must be used on the treatment area prior to making the entry point with the introductory needle; use of anesthesia is optional for the cheek treated with needle only. The TI will inject VOLUMA XC in the mid-face to correct mid-face volume deficit. [REDACTED]
 
[REDACTED]
 
At 1 and 3 months after treatment, subjects will return for a visit during which the EI will rate subjects on the MFVDS for the overall mid-face area, [REDACTED] the TI will record any adverse events (AEs), and subjects will complete the Satisfaction with Cheeks module of the FACE-Q questionnaire. Subjects will be exited from the study at the end of the Month 3 visit.

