
DIAGNOSIS AND CRITERIA FOR INCLUSION/EXCLUSION: Adults with age-related volume deficit in the mid-face who are seeking to increase facial volume in the mid-face.
 
INCLUSION:
 
 1. 35 to 65 (inclusive) years of age and in good general health 2. Has overall mid-face severity of Moderate (3) for both cheeks, Significant (4) for both cheeks, or Severe (5) for both cheeks on the 6-point photonumeric MFVDS as assessed by the EI 
[REDACTED]

Approval Date: 19-Oct-2017

EXCLUSION:

[REDACTED]

8. Has experienced trauma to the mid-face area within 6 months before enrollment or has residual deficiencies, deformities, or scarring

[REDACTED]

10. Has a history of anaphylaxis or allergy to lidocaine (or any amide-based anesthetics), HA products, or Streptococcal protein, or is planning to undergo allergen desensitization therapy during the term of the study

11. Has active autoimmune disease

12. Has current cutaneous or mucosal inflammatory or infectious processes (eg, acne, herpes, gum disease), abscess, an unhealed wound, or a cancerous or precancerous lesion, above the subnasale

[REDACTED]

TEST PRODUCT, DEVICE VOLUME, AND MODE OF ADMINISTRATION:

VOLUMA[®] XC (a hyaluronic acid injectable gel with lidocaine) will be administered via [REDACTED] cannula and [REDACTED] needle to the mid-face to correct mid-face volume deficit. Appropriate injection volume for the mid-face will be determined by the T[REDACTED]

DURATION OF STUDY: Treatment period: 1 day. Follow-up period: 3 months

Approval Date: 19-Oct-2017

RESPONSE MEASURES:

Effectiveness: The primary effectiveness measure is the blinded EI’s assessment of the subject’s overall mid-face volume deficit for each cheek on the MFVDS. The timepoint for the primary effectiveness endpoint is Month 1. The secondary effectiveness measure is the FACE-Q Satisfaction with Cheeks questionnaire evaluated by the subject.

Safety: Safety measures include the presence and severity of injection site responses (ISRs), which will be recorded by the subject in the subject diary for 30 days after treatment, procedural pain assessments, and any adverse events (AEs). Location of these assessments will be noted as being on the right and/or left cheek or not applicable.

STATISTICAL METHODS:

[REDACTED]

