Effectiveness analyses: For the primary effectiveness analysis of change from baseline (screening) to Month 1 in overall mid-face MFVDS, the mean paired difference between treatment with cannula and treatment with needle and its 95% CI based on paired t-test will be calculated. If the upper confidence limit is < 0.5, statistical non-inferiority will be concluded.

[REDACTED]

[REDACTED]

[REDACTED]

Safety analyses: ISRs, procedural pain assessment, and AEs will be summarized using descriptive statistics. ISRs and, separately, AEs will be summarized by the percentage (and 95% CI) of subjects who have the ISR (or AE) on both sides, by the percentage (and 95% CI) of subjects who have the ISR (or AE) on the cannula side and not on the needle side, and by the percentage (and 95% CI) of subjects who have the ISR (or AE) on the needle side and not on the cannula side. Also, the within-treatment percentage (and 95% CI) of subjects who have the ISR (or AE) will be summarized for the cannula side and, separately, for the needle side.

Approval Date: 19-Oct-2017

Table of Contents

Synopsis 3

Table of Contents 6

List of Tables 9

List of Figures 9

1. Abbreviations and Terms 11

█ [REDACTED]

█ [REDACTED]

█ [REDACTED]

2.3 Clinical Rationale 13

3. Study Objectives and Clinical Hypotheses 13

3.1 Study Objectives 13

3.2 Clinical Hypotheses 14

4. Study Design 14

4.1 Structure 14

4.2 Duration 14

4.3 Treatment Groups and Treatment Regimen 14

4.3.1 Study Treatment 14

4.3.2 Control Treatment 14

4.3.3 Methods for Blinding 14

4.4 Permissible and Prohibited Medications/Treatments 15

4.4.1 Permissible Medications/Treatments 15

4.4.2 Prohibited Medications/Treatments 15

4.4.3 Special Diet or Activities 16

4.5 Treatment Allocation Ratio and Stratification 16

5. Study Population 16

5.1 Number of Subjects 16

5.2 Study Population Characteristics 16

5.3 Inclusion Criteria 17

5.4 Exclusion Criteria 17

█ [REDACTED]

█ [REDACTED]

Approval Date: 19-Oct-2017

9.1.2	Instructions for Use and Administration	30
9.1.3	Treatment Regimen Adjustments	31
9.2	Other Study Supplies	31
10.	Study Administration Procedures	31
10.1	Subject Entry Procedures	31
10.1.1	Overview of Entry Procedures	31
10.1.2	Informed Consent and Subject Privacy	32
10.1.3	Method for Assignment to Treatment Groups	32
10.2	Compliance with Protocol	33
10.3	Pregnancy	33
10.4	Study Termination	33
11.	Adverse Events	34
11.1	Definitions	35
11.1.1	Adverse Event	35
11.1.2	Serious Adverse Event	36

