4.5 Treatment Allocation Ratio and Stratification

Subjects will be randomized in a 1:1 ratio to receive treatment on the first side with the cannula or needle.

5. Study Population

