10.1.3 Method for Assignment to Treatment Groups

All subjects will have 1 cheek treated with VOLUMA XC injectable gel using a [REDACTED] cannula and the contralateral cheek treated using a [REDACTED] needle. The side of treatment (ie, side of face for needle or cannula) will be randomized based on a central randomization schedule. An automated IWRS will be used to manage the randomization assignment based on a randomization scheme prepared by Allergan. Study treatments will be labeled with kit numbers. The IWRS will provide the site with the specific kit number(s) for each randomized subject at the time of randomization. Sites will dispense treatment according to the IWRS instructions provided by the system. Kit numbers used for actual injection should be recorded on eCRFs in order to determine "as-treated" versus "as-randomized" treatment association.

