4.1.1 Overall Design

This is a prospective, multicenter, evaluator-blind, randomized, within-subject, controlled, paired-comparison study of the safety and effectiveness of VOLUMA XC injectable gel using a cannula versus needle for cheek augmentation to correct age-related volume deficit in the midface.

Subjects eligible for study enrollment should have cheeks that are either moderate for both cheeks, significant for both cheeks or severe for both cheeks, as assessed by the EI using the 6-point photonumeric Mid-Face Volume Deficit Scale (MFVDS), ranging from 0-5 (0 = none, 1 = minimal, 2 = mild, 3 = moderate, 4 = significant, 5 = severe).

Eligible subjects will be randomized to undergo treatment with cannula in the right or left cheek and with needle in the other cheek (ie, treatment groups will be "cannula left and needle right" or "needle left and cannula right). Prior to randomization, the subjects' demographic information and cosmetic, medical, surgical and dental history will be recorded. Physical measurements and vital signs will be collected, and a urine pregnancy test will be conducted for women of childbearing potential.

The Treating Investigator (TI) and subject will not be blinded to treatment assignment. The Evaluating Investigator (EI) is to remain blinded to treatment assignments for each cheek throughout the duration of the study. Hence, this is considered to be a single-blind study, although some measurement variables are unblinded (eg, injection ease rated by the treating investigator and procedural pain rated by the subject).

diary for 30 days after the treatment session beginning on the day of treatment. Subjects will

return 1 month after treatment, and the TI will evaluate the treatment areas for localized reaction and will review the safety diary with the subject and discuss reported symptoms.

Subjects will attend follow-up visits for safety and effectiveness at Months 1 and 3 after treatment. Safety and effectiveness assessments will be performed at posttreatment follow-up visits. The EI will rate subjects on the MFVDS for each cheek, the TI (or designee other than EI) will record any adverse events (AEs), and subjects will complete the Satisfaction with Cheeks module of the FACE-Q questionnaire. At the month 3 visit, a urine pregnancy test will be performed for female subjects of childbearing potential. Subjects will be exited from the study at the Month 3 visit after study procedures are completed.

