5.1.3.1 Primary Effectiveness Analysis

For the primary effectiveness analysis of change from baseline at Month 1 in EI-assessed overall MFVDS, the mean paired difference between treatment with cannula and treatment with needle,

and its 95% CI based on the paired t-test will be calculated. If the upper confidence limit is less than 0.5, statistical non-inferiority will be concluded.

[figure not shown]

Table 5-15 Primary Effectiveness Analyses

Endpoint	Description	Timing	Methodology		
MFVDS change from	Compare mean difference in the	Baseline and change	Continuous		
baseline to month 1	MFVDS change from baseline score	from baseline to	descriptives with		
	between cannula and needle at Month	months 1	paired-comparison		
	1,		CI		

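### The deciding paired t-test has no readable term for the side/order factor that the trial randomizes 1:1; adding one is a cheap improvement, not the correction of an error

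*Protocol*

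**What the plan says.** Three places give the same deciding analysis. Protocol 8.3.1 states "the mean paired difference between treatment with cannula and treatment with needle, and its 95% CI based on the paired t-test will be calculated". The Synopsis repeats it ("the mean paired difference between treatment with cannula and treatment with needle and its 95% CI based on paired t-test will be calculated"), and so does SAP 5.1.3.1 ("its 95% CI based on the paired t-test will be calculated"). In each, non-inferiority is concluded if the upper limit is below 0.5, and none names a covariate.

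On the design, the Synopsis says "The left side of face will be treated first for all subjects". Protocol 4.5 says "Subjects will be randomized in a 1:1 ratio to receive treatment on the first side with the cannula or needle", and SAP 4.1.1 says "Eligible subjects will be randomized to undergo treatment with cannula in the right or left cheek and with needle in the other cheek". Allocation is central: "An automated IWRS will be used to manage the randomization assignment based on a randomization scheme prepared by Allergan" (Protocol 10.1.3). The readable text gives no block size and no stratification.

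Elsewhere the primary endpoint is to be summarized by baseline score and by site (Protocol 8.4), and the paired difference is modelled on site by ANOVA (SAP 5.1.1.5). No readable passage adjusts for side or order, or breaks the primary result down by it.

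**The concern.** Because left always comes first, which cheek gets the cannula and which instrument is used first are the same two-level factor, and it is what the trial randomizes. An analysis that follows the randomization would normally carry a term for it. Site, which is not randomized, gets a model in the SAP.

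Suppose one cheek responds differently from the other, through anatomy, the injector's handedness or order of treatment. The paired difference then has one mean when the cannula is on the left and another when it is on the right. A single-sample t-test treats that separation as noise. Success rests on one confidence limit, so any avoidable width, or any chance shift from an uneven split, acts directly on the decision.

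**Working it through.** **Inputs from the documents.** 60 treated subjects (Protocol 5.1); margin 0.5 grade; upper limit of a two-sided 95% CI; 1:1 allocation of side.

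**Inputs assumed.** SD of the paired difference within a side group, s = 0.5 to 1.3. Side/order effect L = 0.1 to 0.3 grade. Neither can be read in the documents.

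**The plan's own figure.** No SD, power or assumed true difference is readable for the 60, so it can be neither reproduced nor contradicted. For scale, at true difference 0 a paired test with n = 60 has power 99.9% at SD 0.75, 96.8% at SD 1.0 and 86.2% at SD 1.25.

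**Model.** Let D be cannula minus needle, and x = +1 if the cannula is on the left, -1 if on the right. Then D = tau + L·x + e, with SD(e) = s.

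- Unadjusted: variance of D is about s² + L². Half-width = t59·√(s² + L²)/√60, with t59 = 2.0010.
- Adjusted (intercept of D on x): half-width = t58·s/√(60(1 - x̄²)), with t58 = 2.0017 and x̄ = (n1 - n2)/60.
- Chance shift of the unadjusted mean: L·(n1 - n2)/60.

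**Interval width at 30/30.** Example, s = 1.0 and L = 0.2: unadjusted 2.0010·√1.04/√60 = 0.2634; adjusted 2.0017/√60 = 0.2584; ratio 1.019.

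| s | adjusted half-width | ratio, L = 0.1 | L = 0.2 | L = 0.3 |
|---|---|---|---|---|
| 0.5 | 0.1292 | 1.019 | 1.077 | 1.166 |
| 0.6 | 0.1551 | 1.013 | 1.054 | 1.118 |
| 0.8 | 0.2067 | 1.007 | 1.030 | 1.068 |
| 1.0 | 0.2584 | 1.005 | 1.019 | 1.044 |
| 1.3 | 0.3359 | 1.003 | 1.011 | 1.026 |

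The upper limit rises by 0.0009 to 0.0025 grade at L = 0.1, 0.004 to 0.010 at L = 0.2, and 0.009 to 0.021 at L = 0.3.

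**Uneven split.** At 33/27 the shift is L·6/60: 0.01, 0.02 or 0.03 grade. At 35/25 it is L·10/60: 0.017, 0.033 or 0.05. Under unrestricted 1:1 allocation (binomial, n = 60) a split of 33/27 or worse has probability 0.519, and 35/25 or worse 0.245. Tight blocking would nearly remove the shift.

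**Power** (%, unadjusted v adjusted, 200,000 simulated trials per cell).

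| case | L = 0.1 | L = 0.2 | L = 0.3 |
|---|---|---|---|
| difference 0, SD 1.0, unrestricted | 96.7 v 96.5 | 96.3 v 96.5 | 95.5 v 96.5 |
| difference 0, SD 1.0, 30/30 | 96.7 v 96.7 | 96.5 v 96.7 | 96.1 v 96.7 |
| difference 0, SD 1.3, unrestricted | 83.2 v 82.8 | 82.6 v 82.8 | 81.6 v 82.8 |
| difference 0, SD 1.3, 30/30 | 83.4 v 83.5 | 82.9 v 83.5 | 82.2 v 83.5 |
| cannula 0.2 worse, SD 0.6, unrestricted | 96.4 v 96.5 | 95.2 v 96.5 | 92.8 v 96.5 |

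The largest gain at true difference 0 is about 1.4 points after allowing for variation between repeat simulations. With L = 0 and unrestricted allocation the term costs 0.2 to 0.7 points at SD 1.0 to 1.3. At SD 0.5 to 0.6 and true difference 0 there is no gain.

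**Type I error** at true difference 0.5. Unadjusted: 2.5 to 2.6% under unrestricted allocation and 1.1 to 2.5% at 30/30. Adjusted: 2.5% throughout.

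**The case against.** The strongest reply is that nothing is broken. The three statements of the test agree and the test is valid. No passage suggests a side effect, and the design points to a small one: inclusion requires equal grades on the two cheeks ("Has overall mid-face severity of Moderate (3) for both cheeks, Significant (4) for both cheeks, or Severe (5) for both cheeks"), and the evaluator is blinded. At L = 0.1 the upper limit moves by at most 0.0025 grade against a margin of 0.5, and under unrestricted allocation at SD 1.0 to 1.3 the term slightly reduces power. The plain test is conservative under an even split, so adjusting makes non-inferiority somewhat easier to conclude. All of this stands, and it limits the point to an optional improvement.

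Four stronger readings are tempting, but the documents do not support them.

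- *The primary result is biased or its error rate inflated.* It is not. Side is randomized, so the estimate is unbiased over allocations, and the unadjusted error rate stays at or below about 2.5 to 2.6%.
- *The plan contains no by-side analysis.* That cannot be said. Material is unreadable after Protocol 8.4, in the opening pages of the SAP, in SAP 5.1.1.3 after its first sentence, in SAP 5.1.5, in Tables 5-2 and 5-17, and at the end of the Table 5-15 description.
- *Showing results by side would reveal whether a side/order effect existed.* With standard error s/√60, the chance of detecting L = 0.1 at the two-sided 5% level is about 33% at SD 0.5, 12% at SD 1.0 and 9% at SD 1.3. Side and order cannot be separated in any case.
- *The power gain approaches 2 points at true difference 0.* A closed-form comparison gives up to 1.9 at SD 1.3, but it sets an unrestricted-allocation variance against a 30/30 adjusted interval. Like for like, the most is about 1.4.

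**Conclusion.** The point holds as a low-priority suggestion. In the readable text, the deciding test does not use the factor that the trial randomizes. Using it would follow the design at almost no cost. The benefit depends on an L and an SD that the documents do not give.

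Over the assumed ranges at 30/30, the unadjusted interval is 0.3 to 1.9% wider at L = 0.1, 1.1 to 7.7% at L = 0.2 and 2.6 to 16.6% at L = 0.3. The largest figures fall at small SDs, where power is near 100% if the instruments are equal. The gain becomes material mainly if the cannula is truly somewhat worse: about 4 points of power at true difference 0.2, SD 0.6, L = 0.3 and unrestricted allocation. The chance shift of up to 0.05 grade (35/25, L = 0.3) matters only if allocation is not tightly blocked, which the readable text leaves open.

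**What to change.** Before database lock, define the primary estimate as the intercept of a regression of the as-treated paired difference (cannula minus needle) on a +1/-1 term for the side that received the cannula. Compare its upper 95% limit (58 df at n = 60) with 0.5. Use the randomized side in the as-randomized sensitivity analysis, and carry the same term into the multiple-imputation and BOCF analyses. Keep the paired t-test as supportive. Declare the change in SAP 5.3, since Protocol 8.3.1 and the Synopsis name the t-test. If the sponsor prefers not to alter the deciding test, the adjusted interval can be added as supportive only. If a by-side analysis already exists in the unreadable text, a cross-reference from SAP 5.1.3.1 may be enough.

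The cost is wording. No new data are needed, because the kit numbers actually used are recorded (Protocol 10.1.3). The statistical price is one degree of freedom and, if L = 0, an interval wider by 0.04% at 30/30, 0.5% at 33/27 and 1.5% at 35/25.

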6.5 Early Discontinuation of Subjects

Each subject reserves the right to withdraw from the study at any time without jeopardy to his/her future medical care. It is recommended that all follow-up procedures scheduled to be performed at the final site visit be performed at the subject's last site visit. Subjects may also be administratively withdrawn if they do not return for follow-up visits. For any subject who withdraws from the study, the date and reason for withdrawal will be recorded on the eCRF. If a treatment-related AE is ongoing at the time of withdrawal, the TI will attempt to follow the subject until the AE has been resolved or follow-up is no longer possible. The TI shall ask for the subject's permission to follow his/her status/condition outside the study.

Randomized subjects who withdraw before treatment will not be replaced by another subject. The subject number and associated randomization number of the withdrawn subject must not be reassigned to a different subject.

If a subject fails to return for 1 or more scheduled study visits, the TI (or designee) will attempt to contact the subject to determine and document the reason the subject has failed to return and to encourage compliance with the study visit schedule.

At regular intervals, the TI (or designee) will record on the eCRF the reasons for which any subjects are discontinued from the study, including subjects who signed the ICF but do not proceed to randomization.

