5.1.1.4 Missing Data

If there are any mITT subjects with missing scores for the primary effectiveness endpoint, the following 2 missing-data handling methods are pre-specified to use for missing-data sensitivity analysis of the primary effectiveness endpoint. For each method, there will be no missing baseline MFVDS, because protocol inclusion criteria 2 requires a score of 3, 4 or 5.

Table 5-3 Missing Data Handling by Endpoint Type

Endpoint type	Timing	Missing Data Handling
Categorical Response	Month 1	 All subjects included (mITT population) Multiple imputation (eg, via SAS procedure MI) within treatment, with 5 imputed datasets, will be applied to subjects with missing post-baseline MFVDS scores, using the following model: Month 1 MFVDS = β₀+β₁ Baseline MFVDS + β₂ Month 3 MFVDS
Categorical Response	Month 1	 All subject included (mITT population) Baseline observation carried forward (BOCF) for subjects
1		with missing post-baseline MFVDS values.

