6.2 Analysis Visit Windows

All scheduled and unscheduled visits with complete dates will be assigned visit windows and used for analysis. However, if a scheduled visit with incomplete date is available with no other visits with complete date during the visit window, then the visit with incomplete date may be used for analysis.

If there are multiple visits occurring within a single visit window with relevant data, the visit closest to the target day will be used in the analysis of the corresponding visit windows. If 2 visits are equal distance to the target day and are the same type of visit, then the later visit will be used.

If a subject's visit falls into the analysis window for a visit other than its nominal visit, but is not selected by the above decision rules, and if the subject had no other visits to represent its nominal visit, then that visit will used for analysis of its nominal visit (eg, a month 1 visit that falls into the month 3 window will instead be used for month 1 analysis if the subject has another visit that is selected for month 3 analysis).

Analysis visit windows for effectiveness endpoints and safety are defined as follows:

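### For a wholly missed Month 1 visit, BOCF enters a paired difference of exactly 0, so it cannot test a non-inferiority pass; a tipping-point analysis is needed

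*Protocol*

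**What the plan says.** Protocol 8.3.1 and SAP 5.1.3.1 set the rule: mean paired difference (cannula minus needle) in change from baseline to Month 1, paired-t 95% CI, non-inferior if the upper limit is below 0.5. A higher MFVDS grade is worse, so a positive difference is unfavourable to cannula.

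The primary analysis uses observed pairs. The introduction to Protocol Section 8 states: "No imputation of missing data is planned, except for sensitivity analyses described in Section 8.3.1" (the only other exception concerns diary days for injection site responses).

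If any mITT subject lacks the primary score, both documents name two methods. The Protocol's second is "Baseline observation carried forward (BOCF) to replace missing Month 1 scores"; SAP Table 5-3 repeats it as "Baseline observation carried forward (BOCF) for subjects" with missing post-baseline values. The other is "Multiple imputation (eg, via SAS procedure MI) within treatment, with 5 imputed datasets", with each Month 1 score modelled on baseline and Month 3 MFVDS. The visible text contains no shifted, worst-case or tipping-point analysis.

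Three further provisions bear on the point:

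- SAP 4.1.1, on the follow-up visits: "The EI will rate subjects on the MFVDS for each cheek".
- Inclusion criterion 2 in the Protocol synopsis: "Has overall mid-face severity of Moderate (3) for both cheeks, Significant (4) for both cheeks, or Severe (5) for both cheeks". Both cheeks therefore start at the same grade, and SAP 5.1.1.4 notes that baseline cannot be missing.
- Protocol 4.3.3: the subject is not blinded to which side received cannula.

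**The concern.** BOCF is usually regarded as harsh because it denies a missing subject any benefit. That holds when the question is improvement over baseline. Here the question is the difference between two sides of the same face. When the whole visit is missed, BOCF denies benefit to both sides equally, so the imputed difference is the no-difference value. In a non-inferiority comparison that favours the claim.

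If the trial passes with some Month 1 pairs missing, the report could cite BOCF agreement as evidence of robustness when that agreement was almost certain in advance. Near the margin, BOCF would make a fragile pass look more comfortable. Multiple imputation (MI) as specified contains no departure unfavourable to cannula, so no visible planned analysis shows how bad the missing differences must be before the claim fails.

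**Working it through.** **Inputs.** From the documents: margin 0.5, paired-t 95% CI, 60 treated (Protocol 5.1), equal baseline grades. Not shown in the documents, so assumed: SD of the paired difference (0.7 in the main example; 0.3 to 1.5 in the grid), observed mean, and number of missing pairs k. The plan shows no figure to reproduce.

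**Step 1: the imputed value.** With baselines B_c and B_n carried forward, the paired difference is (B_c − B_c) − (B_n − B_n) = 0, whatever the baseline.

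**Step 2: effect on the limit.** With n = 60 − k observed pairs, mean m and SD s:

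- Observed limit = m + t(0.975, n−1)·s/√n.
- After BOCF (k zeros added, N = 60): M = nm/N; SS = (n−1)s² + nm² − NM²; limit = M + t(0.975, N−1)·√(SS/(N−1))/√N.

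Example with m = 0.28, s = 0.7, k = 6:

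- Observed: 0.28 + 2.006 × 0.7/√54 = 0.471.
- BOCF: M = 54 × 0.28/60 = 0.252; SS = 25.970 + 4.234 − 3.810 = 26.393; SD = √(26.393/59) = 0.669; limit = 0.252 + 2.001 × 0.669/√60 = 0.425.

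**Step 3: shift that would reverse the pass.** The paired difference is multiply imputed from a normal model with posterior draws of mean and variance, and a shift δ is added to each imputed value. With many imputations:

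- e = (n−1)s²/(n−3)
- between-imputation variance B = (k/N)²·e·(1/n + 1/k)
- within-imputation variance W = [(n−1)s² + ke + (nk/N)δ²]/[N(N−1)]
- limit = m + kδ/N + t·√(W + B), with small-sample Rubin degrees of freedom.

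In the example, e = 0.509 and B = 0.00094. At δ = 0.27, W = 0.00831, df = 51.3 and t = 2.007, so the limit is 0.307 + 2.007 × √0.00925 = 0.500. At δ = 0 it is 0.472.

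| SD | Missing | Mean | Observed limit | BOCF limit | Shift to reach 0.5 |
|---|---|---|---|---|---|
| 0.7 | 6 | 0.28 | 0.471 | 0.425 | +0.27 |
| 0.7 | 6 | 0.20 | 0.391 | 0.352 | +0.94 |
| 0.7 | 6 | 0.10 | 0.291 | 0.262 | +1.68 |
| 0.7 | 6 | 0 | 0.191 | 0.171 | +2.35 |
| 0.7 | 6 | −0.30 | −0.109 | −0.097 | +4.20 |
| 0.7 | 3 | 0.28 | 0.466 | 0.443 | +0.61 |
| 0.7 | 3 | 0.20 | 0.386 | 0.367 | +1.77 |
| 0.7 | 3 | 0.10 | 0.286 | 0.271 | +2.97 |
| 0.7 | 3 | 0 | 0.186 | 0.176 | +4.07 |
| 1.0 | 6 | 0.20 | 0.473 | 0.425 | +0.25 |

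**Step 4: can BOCF overturn a pass?** Grid of means −1 to 1 (201 values), SDs 0.3 to 1.5 (25 values) and k = 1 to 12, giving 60,300 settings. Of these, 37,731 pass on observed pairs and BOCF overturns 0. It raises the limit in 22,752, all with an observed limit of 0.0013 or less. It lowers the limit in the other 14,979, including all 3,000 with an observed limit between 0.4 and 0.5. A wider grid (means −5 to just under 0.5, SDs up to 5, up to 20 missing) gave 747,651 passes and no reversal.

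**Step 5: at the margin.** With a true difference of 0.5 (SD 0.5, 0.7 or 1.0; 1, 3 or 6 missing; 200,000 simulated trials per setting), the primary analysis passed 4,863 to 5,144 times (2.4% to 2.6%), and BOCF agreed every time. Requiring BOCF agreement therefore filters out none of these false passes.

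**The case against.** No decision turns on this. The primary test uses observed pairs, and its error rate is untouched. That stands.

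Missing pairs may also be few. On withdrawal, Protocol 6.5 says: "It is recommended that all follow-up procedures scheduled to be performed at the final site visit be performed" at the last visit. SAP 6.2 adds: "All scheduled and unscheduled visits with complete dates will be assigned visit windows and used for analysis". The Month 1 window runs from Day 2 to Day 61, and a late Month 1 visit can be mapped back. That also stands; three or six missing is an assumption.

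Even then it matters only near the margin. With SD 0.7 and six missing, the observed limit falls between 0.4 and 0.5 in 1.4% of trials if the techniques are equal and 11% if the true difference is 0.1. With SD 0.5 both are below 1%. But the figure is 33% for a true difference of 0.2 with SD 0.7, and 13% for no difference with SD 1.0, so the region cannot be dismissed.

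MI is a second check. It uses each cheek's Month 3 score, so a worse cannula cheek seen then is carried in. This narrows the gap, but does not close it when Month 3 is missing too. The shifts above come from imputing the paired difference, not from the SAP's within-treatment model, and do not describe that model. If only one cheek's score is missing, the BOCF difference need not be 0.

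Finally, some text is redacted. Since both documents say there are two methods and name them, a hidden third is unlikely.

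**Conclusion.** The concern holds. For a wholly missed Month 1 visit, the zero difference is exact and needs no assumption. It pulls the upper limit toward 0, and no passing setting examined was reversed. BOCF agreement therefore carries almost no information about robustness.

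The practical size depends on the assumed SD, mean and missingness. With an observed limit of about 0.47, shifts of +0.25 to +0.61 grade bring it to 0.5 while BOCF shows a lower limit than the observed one. With a mean at or below 0, the shift exceeds +2 grades and the flaw is immaterial. This is a gap in the supporting analyses, not an error in the primary test, and it is cheap to close.

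**What to change.** In SAP Table 5-3, add a tipping-point analysis to be run whenever any mITT subject lacks the Month 1 pair, and record the addition in SAP 5.3 before database lock. The change to the per-protocol definition was recorded there in the same way, so Protocol 8.3.1 need not be amended; the entry should acknowledge that this is a third method beyond the two listed.

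- Multiply impute the paired difference, or both cheeks jointly with one record per subject, with proper parameter and residual variance. Imputing each cheek separately drops the between-cheek correlation and widens the interval, which is conservative but avoidable.
- Add a shift against cannula in steps of 0.1 from 0 until the upper limit reaches 0.5 or the mean imputed difference reaches +5. With equal baselines on a 0 to 5 scale, +5 is the largest possible difference.
- Report that shift and the number of missing pairs.
- Use at least 200 imputations, a fixed seed, and the same imputations at every shift. In the 0.28, six-missing example, 5 imputations give a rerun SD of 0.018 in the limit (5th to 95th percentile 0.448 to 0.506), against about 0.010 for one 0.1 step. The SD is 0.005 with 50 imputations and 0.003 with 200.
- Keep BOCF as a descriptive display and do not cite it as support for robustness.

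The cost is a short SAP addition and slight extra programming, with no new data. The sensitivity result may look less favourable than under BOCF.
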